**Table 2: Prohibited Medications with potential for drug-drug interaction****Single Agents:**

P-glycoprotein	CYP3A4		CYP2D6
Clarithromycin	Clarithromycin	Ritonavir	bupropion
Erythromycin	Telithromycin	Saquinavir	fluoxetine
Amiodarone	Troleandomycin	Telaprevir	fluvoxamine
Digitalis	Nefazodone	Tipranavir	paroxetine
Dronedarone	St. John's wort	chloramphenicol	Quinidine
Carvedilol	Itraconazole	Rifampin	Terbinafine
Propafenone	Ketoconazole	Cobicistat	
Quinidine	Posaconazole	grapefruit juice	
Ranolazine	Voriconazole	conivaptan	
Verapamil	Atazanavir	Diltiazem	
Sildenafil	Boceprevir	Idelalisib	
Itraconazole	Darunavir	enzalutamide	
Ketoconazole	Indinavir	Mitotane	
Ritonavir	Lopinavir	carbamazepine	
Saquinavir	Nelfinavir	Phenytoin	
Telaprevir			
Lapatinib			

**Combination Agents:**

P-glycoprotein	CYP3A4
lopinavir and ritonavir	danoprevir and ritonavir
saquinavir and ritonavir	elvitegravir and ritonavir
tipranavir and ritonavir	indinavir and ritonavir
	lopinavir and ritonavir
	paritaprevir and ritonavir and (ombitasvir and/or dasabuvir)
	saquinavir and ritonavir
	tipranavir and ritonavir

Source:

<https://www.fda.gov/Drugs/DevelopmentApprovalProcess/DevelopmentResources/DrugInteractionsLabeling/ucm093664.htm> (Tables 2-2, 2-3, 3-2, 3-3, and 5-2)

## 7. STUDY INTERVENTION DISCONTINUATION AND PARTICIPANT DISCONTINUATION/WITHDRAWAL

### 7.1. Decrease in dose of study drug

Subjects who have their dose of study drug decreased will be monitored closely with serum alkaline phosphatase, aminotransferases and bilirubin levels being measured every 2 to 4 weeks. Elevations in ALP or bilirubin will be promptly recognized by the site PI and by the medical monitor because this is an open label study. If subjects are deemed to be treatment failures when their dose of study drug is decreased, study drug will be discontinued (see Section 7.2).

### 7.2. Discontinuation of Study Intervention

HTD1801 treatment must be discontinued for a subject if any of the following criteria are met.

- Adverse event that may jeopardize subject's safety
- Grade 3 and above adverse events (AEs) for which the causality is considered as related to investigational agent
- Discontinuation due to drug-induced liver injury (refer to Section 10)
- Request by the subject
- Pregnancy

For subjects who discontinue investigational study drug, an Early Termination Visit should be conducted at the time the investigational study drug is discontinued (see Section 7.3). Subjects who terminate from the study prior to Study Visit Week 12 will be requested to return to the clinic 28 days **after the date of last dose** of investigational study drug and complete the equivalent of the Week 16 follow up visit assessments. If necessary, arrangements can be made with the site and the subject to conduct the visit virtually and make use of a local laboratory for the study required Study Visit Week 16 lab tests.

### 7.3. Participant Discontinuation/Withdrawal from the Study

Subjects may be discontinued from the study for any of the following reasons:

- Noncompliance
  - Failure to receive study medication or treatment
  - Failure to comply with protocol requirements
  - Unauthorized, subject-initiated changes in dosing regimen
- Withdrawal of consent
  - Any subject who withdraws consent for any reason at any time during the study will be discontinued from the study, and the reason(s) will be documented on the appropriate eCRF page.
- Lost to Follow-Up

- For subjects who cannot be contacted for either a return for a scheduled clinic visit or for follow-up assessments as described, and who may be considered “lost to follow-up,” at least 3 documented attempts should be made to establish contact with and to instruct the subject on how to complete study procedures. In the final attempt to contact the subject, a letter should be sent by certified mail to the subject’s last known address
- Adverse Events
  - Study drug will be discontinued in an individual subject if the subject experiences a grade 3 and above adverse event (AE) for which the causality is considered as related to investigational study drug
- Treatment Failure
  - If any subject fails treatment after having their dose of HTD1801 reduced, their participation in the study will be ended and they will be allowed to resume their pre-study treatment for PBC. A subject will be deemed to have failed treatment if serum ALP, after having been lowered on initial treatment, returns to baseline or higher on two subsequent occasions (baseline being the average of the historical value and the value at screening).

#### **7.4. Study Stopping Criteria**

If there is one death (grade 5 AE) or two subjects meeting the same grade 4 AE (life threatening or disabling AE), or three subjects meeting the same grade 3 AE (severe AE), the trial will be paused and the AEs assessed for causality. The event data will be submitted to the FDA with a request to resume conduct of the trial.

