The Investigator is responsible for all AE assessments. The Investigator and investigational site staff will note all AEs mentioned by the subject at Screening, Baseline and during study drug administration. All clinical complaints volunteered by or elicited from the subject during the study will be recorded on the appropriate page of the eCRF for the study period indicated. The subject will receive appropriate treatment and medical supervision for any AE that occurs.

All AEs judged to be clinically significant, including clinically significant laboratory abnormalities, will be followed until resolution. All AEs will be summarized in the clinical study report and the annual report or more frequently if requested by the regulatory agency. Serious adverse events require special reporting in addition to documentation in the eCRF as described in Section 9.3.6.

The severity of adverse events will be assessed according to Common Terminology Criteria for Adverse Events (CTCAE) version 5.0.

([https://ctep.cancer.gov/protocoldevelopment/electronic\\_applications/docs/ctcae\\_v5\\_quick\\_reference\\_5x7.pdf](https://ctep.cancer.gov/protocoldevelopment/electronic_applications/docs/ctcae_v5_quick_reference_5x7.pdf))

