**Table 4 Classification of Adverse Events (AEs) by Severity**

Severity a	Definition
Mild AE (Grade 1)	Mild; asymptomatic or mild symptoms; clinical or diagnostic observations only; intervention not indicated.
Moderate AE (Grade 2)	Moderate; minimal, local or noninvasive intervention indicated; limiting age-appropriate instrumental activities of daily living
Severe AE (Grade 3)	Severe or medically significant but not immediately life-threatening; hospitalization or prolongation of hospitalization indicated; disabling; limiting self care activities of daily living
Life-threatening or disabling AE (Grade 4)	Life-threatening consequences; urgent intervention indicated.
Death related to AE (Grade 5)	Death related to AE.

a From Common Terminology Criteria for Adverse Events, Version 5.0

Any AE that changes in severity or grade during a single occurrence of an AE will be recorded in the eCRF at the highest level experienced by the subject.

An AE that is assessed as severe should not be confused with an SAE. Severity is a category used for rating the intensity of an AE (such as mild, moderate, or severe myocardial infarction). However, an AE itself may be of relatively minor medical significance, such as a severe headache. Both AEs and SAEs can be assessed as severe. An AE is considered serious when it meets one of the predefined outcomes described in Section 9.3.2.

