An overview of AEs, which includes subject incidence of TEAEs, treatment-related TEAEs, serious TEAEs, AESIs, TEAEs by CTCAE grade and TEAEs leading to permanent discontinuation of treatment. For TEAEs presented by CTCAE grade, the worst grade during the clinical study will be presented for each subject.

The subject incidence of TEAEs, treatment-related TEAEs and TEAEs leading to permanent discontinuation of treatment will be summarized by system organ class and preferred term.

HighTide Biopharma Pty. Ltd.
Protocol HTD1801.PCT013

TEAEs will also be summarized in a table by CTCAE grade. For TEAEs presented by CTCAE grade, the worst grade for each event during the clinical study will be presented for each subject. A listing for all off-treatment AEs will be presented similarly.

All AEs will be presented as a listing by subject. TEAEs leading to treatment discontinuation will be provided in a separate listing.

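### The study pause rule in Protocol 7.4 does not say that a Grade 4 event counts toward the Grade 3 limb, so read literally it pauses on Grades 3, 3, 3 but not on 3, 3, 4

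*Protocol*

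**What the plan says.** Protocol 7.4 (Study Stopping Criteria) has three limbs. The trial is paused after one death, or after "two subjects meeting the same grade 4 AE (life threatening or disabling AE), or three subjects meeting the same grade 3 AE (severe AE"). Causality is assessed after the pause, and the event data go to the FDA with a request to resume. The Grade 3 and Grade 4 limbs each name a single grade.

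The rules for individual subjects use threshold wording. Protocol 7.2 stops drug for "Grade 3 and above adverse events (AEs) for which the causality is considered as related to investigational agent". Protocol 7.3 says "Study drug will be discontinued in an individual subject if the subject experiences a grade 3 and above adverse event (AE"), again for events judged related.

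Two further provisions deal with recording and reporting. The text under Protocol Table 4 says that an event whose grade changes "will be recorded in the eCRF at the highest level experienced by the subject". For the table of treatment-emergent events by grade, SAP 3.4.1 says that "the worst grade for each event during the clinical study will be presented for each subject". The SAP contains no pause rule of its own.

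**The concern.** A stopping rule for safety should be monotone: making one event in a set worse should never remove a pause that the milder set would have triggered. With two separate single-grade counts, 7.4 can fail this. Take three subjects with the same event at Grade 3, and suppose one of them had reached Grade 4 instead. The Grade 3 count falls to two and the Grade 4 count is only one, so no limb is met.

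What is at stake is the mandatory element. Section 7.4 is the only rule in the documents that forces a pause from a count across subjects, and it does so before causality is judged. If it is not triggered, stopping to review the cluster is left to discretion.

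**Working it through.** **Inputs.** The pause thresholds of one, two and three come from Protocol 7.4. The maximum of 30 subjects comes from Protocol 4.1. Protocol 12.4.7 and SAP 2.8 allow enrolment to end below 30, and SAP 2.8 places an interim summary when 15 subjects have reached Week 12. N = 15 is therefore used as a second illustrative size. The documents state no operating characteristic for the pause rule and no Grade 3 or Grade 4 rate for any event term, so there is no plan figure to reproduce and every rate below is assumed.

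**Step 1: logic.** For one event term, let n3 and n4 be the numbers of subjects whose highest grade is 3 or 4, with no death.

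- Literal rule: pause if n4 ≥ 2 or n3 ≥ 3.
- 'Or higher' rule: pause if n4 ≥ 2 or n3 + n4 ≥ 3.

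The rules disagree only when n4 ≤ 1, n3 ≤ 2 and n3 + n4 ≥ 3. The only solution is n3 = 2, n4 = 1. Any death pauses the trial under both rules. Listing all 55 sets of Grades 3, 4 and 5 in one to five subjects gives the same answer: only {3, 3, 4} changes outcome.

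| Same event, grades | Literal 7.4 | Grade 3 limb 'or higher' |
|---|---|---|
| 3, 3, 3 | pause | pause |
| 3, 3, 4 | **no pause** | **pause** |
| 3, 4, 4 | pause | pause |
| any set with a 5 | pause | pause |

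**Step 2: size.** With independent subjects and per-subject rates p3 and p4 for one event term,

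P(n3 = 2, n4 = 1) = C(N,2) × (N − 2) × p3² × p4 × (1 − p3 − p4)^(N − 3).

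The multiplier C(N,2) × (N − 2) is 435 × 28 = 12,180 for N = 30 and 105 × 13 = 1,365 for N = 15.

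- N = 30, 1%/0.2%: 12,180 × 0.01² × 0.002 × 0.988^27 = 0.002436 × 0.7218 = 0.0018.
- N = 30, 3%/1%: 12,180 × 0.03² × 0.01 × 0.96^27 = 0.10962 × 0.3321 = 0.0364.
- N = 15, 1%/0.2%: 1,365 × 0.01² × 0.002 × 0.988^12 = 0.000273 × 0.8651 = 0.0002.
- N = 15, 3%/1%: 1,365 × 0.03² × 0.01 × 0.96^12 = 0.012285 × 0.6127 = 0.0075.

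| Assumed Grade 3 / Grade 4 rate | N = 30 | N = 15 |
|---|---|---|
| 1% / 0.2% | 0.18% | 0.02% |
| 2% / 0.5% | 1.2% | 0.20% |
| 3% / 1% | 3.6% | 0.75% |

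As a check, the total probability of a pause on that term at 3%/1% and N = 30 is 0.0944 under the literal rule and 0.1308 under the 'or higher' rule. The difference is 0.0364, which matches the formula.

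As estimates of how often the literal rule would never pause when the other would, these are upper bounds. If the subject who finished at Grade 4 had first been counted as the third case at Grade 3, the trial would already have paused.

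**The case against.** The strongest reply is that the defect depends on a reading. Section 7.4 speaks of subjects meeting a grade, and an event at Grade 4 can be said to have met Grade 3 on the way. The tiers of one, two and three show that worse events were meant to need fewer cases. On that reading there is no gap. This has force: it is a sensible account of the intent. But the text does not state it, and sites and the sponsor should not have to infer how a mandatory trigger counts.

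A reader might go further the other way and infer that the plan deliberately keeps Grade 4 events out of the Grade 3 count, citing the threshold wording in 7.2 and 7.3 and the highest-grade provisions. The documents do not support that. Sections 7.2 and 7.3 use a single limb and need threshold words to reach Grades 4 and 5, whereas 7.4 gives each grade its own limb, so the omission there is natural. The text under Table 4 governs eCRF entry and SAP 3.4.1 governs tabulation. Neither defines how 7.4 counts.

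The second reply is that a 3, 3, 4 cluster would hardly go unnoticed. Section 7.2 stops drug in a subject with a related event of Grade 3 or worse, or with any event that may jeopardize safety. A life-threatening event is an SAE and is reported within 24 hours (9.3.6). The study may be suspended for unacceptable risk (13.2). One further Grade 3 case, one further Grade 4 case or any death closes the gap. All of this stands and lowers the consequence. None of it forces a pause: the first two act on single subjects or single reports, and 13.2 is discretionary.

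**Conclusion.** The point holds as a wording gap of minor severity. Read literally, 7.4 is not monotone at exactly one combination, two subjects at Grade 3 and one at Grade 4 of the same event, and no other provision requires a pause there.

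The size rests on assumed rates, independent subjects and one event term at a time. Over 1%/0.2% to 3%/1% the chance of ending on that combination is about 0.2% to 3.6% at N = 30, which is the enrolment ceiling, and 0.02% to 0.75% at N = 15. A reader might try higher assumed rates, or divide the gap by the small probability of any pause, and conclude that the rule often fails. The documents offer no rates to support such a claim, and a large share of a rare event is still rare. Nor does the gap leave subjects unprotected, given the safeguards in 7.2, 9.3.6 and 13.2. The case for changing the text is that the trigger is mandatory and its meaning should be certain, not that a missed pause is likely.

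**What to change.** Change the Grade 3 limb of Protocol 7.4 to: *three or more subjects with the same AE at Grade 3 or higher*. The death and Grade 4 limbs need no change. In particular, adding 'or higher' to the Grade 4 limb would have no effect, because one death already pauses the trial. The counts of one, two and three stay as they are, and no pause that the present wording triggers is lost.

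The cost is one sentence. Because it bears on subject safety, it is a substantive change under Protocol 13.5 and needs an amendment with IRB/IEC approval and regulatory submission. It could go into the next amendment. The operational downside is possibly an earlier pause. If the threshold reading was always intended, the edit changes nothing in practice and only removes the doubt.

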## **8. STUDY PROCEDURES AND EVALUATIONS**

Study procedures are summarized across all scheduled study visits as indicated in the Study Schema (Section 1.2) and Table 1 Schedule of Activities (Section 1.3). Unscheduled visits may also occur at any time if medically warranted. Study related assessments performed at all visits will be recorded in the eCRF.

Refer to Section 11 for COVID-19 contingency measures for Study Visit Week 2, 4, 8, 16 and ET in case a subject is unable or unwilling to participate in an on-site visit due to the COVID-19 pandemic.

### **8.1. Pre-screening (Days -56 to -28) ALP**

Prior to any clinical procedures and evaluations, written signed informed consent must be obtained. If the historical ALP that was obtained as part of standard of care is not  $\geq 1.5 \times$  ULN or is not within 6 months of the screening visit, a pre-screening visit must be conducted in order to collect a chemistry lab sample to determine the ALP value using the central laboratory.

Informed consent needs to be obtained from the subject before proceeding with any study-specific procedures. The pre-screening ALP sample through the central laboratory needs to be obtained at least 28 days prior to full screening visit.

- Informed consent
- Assign subject ID#
- Chemistry sample for alkaline phosphatase

### **8.2. Screening (Days -28 to -1)**

Screening procedures must be completed within 28 days prior to the Baseline visit and can be performed across multiple days during this period. Screening clinical laboratory tests may be repeated once during Screening if the Investigator believes the results to be erroneous. In the event that Screening tests are repeated, the most current results will be used to determine eligibility. If screening procedures are completed and subject eligibility is confirmed, the full 28-day screening period may not be necessary.

During Screening, the following procedures must be conducted and assessments obtained. The information will be collected in the investigational site's standard source documents or in source document templates provided by the Sponsor.

- Informed consent if not obtained at pre-screening visit
- Confirm eligibility criteria
- Demographic information
- Medical history
- Assign subject ID # if not obtained at pre-screening visit
- Complete physical examination
- Vital signs
- Weight, height
- Electrocardiogram, 12 lead (ECG)

- Serum chemistry panel including GGT, Lipid panel — fasting, unsweetened clear coffee, tea or water permitted but no food after supper the evening before
- Complete blood count (CBC) with differential (no smear)
- INR
- Fibrinogen
- CRP
- Haptoglobin
- ELF
- G6PD
- IgM
- IgG
- AMA
- ANA
- TSH
- FSH (if needed to confirm menopausal status)
- Pruritus VAS
- Prior and concomitant medications

Subjects will be instructed to stop all prohibited medications (see Section 6.4) prior to beginning Baseline procedures. In particular, subjects will be cautioned against the use of UDCA until their participation in this study is complete.

NOTE: If the screening ALP value is more than  $\geq 30\%$  lower than the historical value obtained as part of standard of care, the subject will not qualify for enrollment but may be re-screened as soon as 4 weeks later. If on re-screening the ALP value continues to be  $> 30\%$  lower, the subject will not be included in the study.

### 8.3. Baseline/Day 0

Potential subjects who have successfully completed all of the Screening procedures and have met all the eligibility criteria (see Sections 5.1 and 5.2) will be eligible for enrollment in the study. Subjects will undergo the following Baseline procedures and assessments prior to the first dose of study drug:

- Confirmation of continued eligibility
- Update of medical history information
- Targeted physical examination (to include assessment of only findings that were abnormal at Screening/Baseline visit and any new symptoms exhibited or volunteered by subject)
- Vital signs
- Weight
- Serum chemistry panel including GGT

- Lipid panel -- fasting, unsweetened clear coffee, tea or water permitted but no food after supper the evening before
- CBC with differential
- Fibrinogen
- CRP
- Haptoglobin
- ELF
- IGM
- IgG
- Bile acid panel
- Urine pregnancy test for women of childbearing potential
- GLOBE Score (calculated by biostatistical programming based upon age, total bilirubin, alkaline phosphatase, albumin and platelet count)
- Pruritus VAS
- Adverse event monitoring
- Concomitant medications
- Dispense study drug

#### **8.4. Week 2 and Week 4 Visits ( $\pm 3$ days)**

Week 2 and Week 4 visits are conducted as in-clinic visits or optional in-home visits. The following procedures and assessments will be conducted at these visits:

- Serum chemistry panel including GGT
- Adverse event monitoring
- Concomitant medications

Refer to Section 11 for COVID-19 contingency measures for Study Visits Week 2 and Week 4 in case a subject is unable or unwilling to participate in an on-site visit due to the COVID-19 pandemic.

#### **8.5. Week 6 Visit ( $\pm 3$ days)**

The following procedures and assessments will be performed during the Week 6 clinic visit:

- Targeted physical examination (to include assessment of only findings that were abnormal at Screening/Baseline visit and any new symptoms exhibited or volunteered by subject)
- Vital signs
- Weight
- Serum chemistry panel including GGT
- Lipid panel - fasting, unsweetened clear coffee, tea or water permitted but no food after supper the evening before

- CBC with differential
- INR
- Fibrinogen
- CRP
- Haptoglobin
- ELF
- IGM
- IgG
- Bile acid panel
- PK blood draw for at least 6 subjects who consent to participate in the PK sub-study
  - PK lab draw at -30 minutes prior to investigational study drug dosing
  - PK lab draw at  $\pm$ 30 minutes 4 hours post investigational study drug dosing
  - PK lab draw at  $\pm$ 30 minutes 8 hours post investigational study drug dosing
- GLOBE Score (calculated by biostatistical programming based upon age, total bilirubin, alkaline phosphatase, albumin and platelet count)
- Pruritus VAS
- Adverse event monitoring
- Concomitant medications
- Return study drug/reconciliation
- Dispense study drug

## **8.6. Week 8 Visit ( $\pm$ 3 days)**

The Week 8 visit is conducted as an in-clinic visit or optional in-home lab visit. The following procedures and assessments will be conducted at this visit:

- Serum chemistry panel including GGT
- Adverse event monitoring
- Concomitant medications

Refer to Section 11 for COVID-19 contingency measures for Study Visit Week 8 in case a subject is unable or unwilling to participate in an on-site visit due to the COVID-19 pandemic.

## **8.7. Week 12 Visit ( $\pm$ 3 days)**

The following procedures and assessments will be performed during the Week 12 clinic visit:

- Targeted physical examination (to include assessment of only findings that were abnormal at Screening/Baseline visit and any new symptoms exhibited or volunteered by subject)
- Vital signs
- Weight
- ECG

- Serum chemistry panel including GGT
- Lipid panel - fasting, unsweetened clear coffee, tea or water permitted but no food after supper the evening before
- CBC with differential
- INR
- Fibrinogen
- CRP
- Haptoglobin
- ELF
- IGM
- IgG
- Bile acid panel
- PK blood draw for at least 6 subjects who consent to participate in the PK sub-study
  - PK lab draw at -30 minutes prior to investigational study drug dosing
  - PK lab draw at  $\pm$ 30 minutes 4 hours post investigational study drug dosing
  - PK lab draw at  $\pm$ 30 minutes 8 hours post investigational study drug dosing
- Urine pregnancy test for women of childbearing potential
- GLOBE Score (calculated by biostatistical programming based upon age, total bilirubin, alkaline phosphatase, albumin and platelet count)
- Pruritus VAS
- Adverse event monitoring
- Concomitant medications
- Return study drug/reconciliation

